12.2.2. Patient Disposition

The number of randomized patients along with mITT and PP set populations will be summarized by treatment group. Frequency counts and percentages in different study parts will be presented for each treatment group. All patients who discontinue from the study or the study treatment will be identified, and the extent of their participation in the study will be reported along with their reason for discontinuation. Reasons for discontinuation from the study will be summarized by treatment group.

12.2.3. Patient Characteristics

Demographic and baseline characteristics will be summarized descriptively by treatment group. Descriptive statistics including number of patients, mean, standard deviation (SD), median, minimum, and maximum will be provided for continuous measures, and frequency counts and percentages will be tabulated for categorical measures. No formal statistical comparisons will be made among treatment groups unless otherwise stated.

12.2.4. Concomitant Therapy

Concomitant medications will be descriptively summarized by treatment group in terms of frequencies and percentages using the mITT population. The medications will be coded accordingly.

12.2.5. Treatment Compliance

Compliance to study treatment for baricitinib and placebo will be assessed through counts of returned study drug tablets. For baricitinib or placebo, a patient will be considered significantly noncompliant if he or she misses more than 20% of the prescribed doses during the study, unless the patient's study drug is withheld by the investigator for safety reasons. Similarly, a patient will be considered significantly noncompliant if he or she is judged by the investigator to have intentionally or repeatedly taken more than the prescribed amount of study drug. Patients who are significantly noncompliant will be excluded from the PP set.

Patient compliance will be further defined in the SAP.

12.2.6. Primary Outcome and Methodology

A logistic regression model with treatment, country and joint erosion status in the model will be used to test the treatment difference between baricitinib and placebo in the proportion of patients achieving ACR20 response at Week 12. The NRI method as described above will be used to impute missing data.

12.2.7. Efficacy Analyses

Secondary analyses:

1. Comparison between baricitinib and placebo in change from baseline to Week 12 in HAQ-DI score: An ANCOVA model with treatment, country, joint erosion status, and baseline score in the model will be used to test the treatment difference between baricitinib and placebo in change from baseline to Week 12 in HAQ-DI. The mBOCF and mLOCF approaches as described above will be used to impute missing data.
2. Comparison between baricitinib and placebo in change from baseline to Week 12 in DAS28-hsCRP: An ANCOVA model with treatment, country, joint erosion status, and baseline score in the model will be used to test the treatment difference between baricitinib and placebo in change from baseline to Week 12 in DAS28-hsCRP. The mBOCF and mLOCF approaches as described above will be used to impute missing data.
3. Comparison between baricitinib and placebo in proportion of patients achieving an SDAI score ≤ 3.3 at Week 12: A logistic regression model with treatment, country, and joint erosion status in the model will be used to test the treatment difference between baricitinib and placebo in the proportion of patients achieving an SDAI score ≤ 3.3 response at Week 12. The NRI method as described above will be used to impute missing data.
4. Comparison between baricitinib and placebo in mean duration of morning joint stiffness in the 7 days prior to Week 12: An ANCOVA model with treatment, country, joint erosion status, and baseline score (Day 1 on the diaries) in the model will be used to test the treatment difference between baricitinib and placebo in mean duration of morning joint stiffness in the 7 days prior to Week 12. Refer to the SAP for more details.
5. Comparison between baricitinib and placebo in mean severity of morning joint stiffness in the 7 days prior to Week 12: An ANCOVA model with treatment, country, joint

erosion status, and baseline score (Day 1 on the diaries) in the model will be used to test the treatment difference between baricitinib and placebo in mean severity of morning joint stiffness in the 7 days prior to Week 12. Refer to the SAP for more details.

6. Comparison between baricitinib and placebo in mean Worst Tiredness NRS in the 7 days prior to Week 12: An ANCOVA model with treatment, country, joint erosion status, and baseline score (Day 1 on the diaries) in the model will be used to test the treatment difference between baricitinib and placebo in mean Worst Tiredness NRS in the 7 days prior to Week 12. Refer to the SAP for more details.
7. Comparison between baricitinib and placebo in mean Worst Joint Pain NRS in the 7 days prior to Week 12: An ANCOVA model with treatment, country, joint erosion status, and baseline score (Day 1 on the diaries) in the model will be used to test the treatment difference between baricitinib and placebo in mean Worst Joint Pain NRS in the 7 days prior to Week 12. Refer to the SAP for more details.

Other efficacy and health outcome analyses:

Besides the analyses listed in the objective section, the following analyses will be performed:

- change from baseline in mTSS
- proportion of patients with mTSS change ≤ 0
- change from baseline in joint space narrowing and bone erosion scores
- proportion of patients achieving DAS28-hsCRP ≤ 3.2 and < 2.6
- proportion of patients achieving HAQ-DI improvement ≥ 0.22 and ≥ 0.3
- proportions of patients achieving ACR20 (other than primary), ACR50, and ACR70
- percentage change from baseline in individual components of the ACR Core Set
- change from baseline in DAS28-hsCRP
- change from baseline in DAS28-ESR
- proportion of patients achieving DAS28-ESR ≤ 3.2 and < 2.6
- change from baseline in HAQ-DI
- change from baseline in CDAI score
- change from baseline in SDAI score
- proportion of patients achieving CDAI score ≤ 2.8
- proportion of patients achieving SDAI score ≤ 3.3 (ACR/EULAR remission according to the Index-based definition)
- proportion of patients achieving ACR/EULAR remission according to the Boolean-based definition
- proportion of patients achieving moderate response and good response based on EULAR response criteria
- hybrid ACR (bounded) response measure
- change from baseline in fatigue score in the FACIT-F
- change from baseline in health states, VAS score, and index score of EQ-5D-5L
- change from baseline in absenteeism, presenteeism, work productivity loss, and activity impairment scores of WPAI-RA
- individual items and total score in healthcare resource utilization

- change from baseline in duration of morning joint stiffness assessed at the visit using an ePRO tablet
- change from baseline in Worst Tiredness NRS assessed at the visit using an ePRO tablet
- change from baseline in Worst Joint Pain NRS assessed at the visit using an ePRO tablet.

Approaches similar to the primary and above secondary analyses will be used to analyze other efficacy and health outcome measures. Analysis methods will consist of ANCOVA and logistic regression, as described above, using mBOCF, linear extrapolation, NRI, and mLOCF missing data imputation methods, where applicable. In addition, continuous secondary parameters that are collected at repeated visits throughout the double-blind period may be analyzed using a MMRM approach as described in Section 12.2.1. The MMRM will be considered as a sensitivity approach to ANCOVA results.

The Study JAGS data of mTSS, joint space narrowing and bone erosion scores will be pooled with JADV data for further analyses.

Data collected after initiation of rescue therapy will be summarized as appropriate. Further details will be provided in the SAP.

12.2.8. Health Outcome Analyses

The health outcomes will be analyzed using methods described for continuous or categorical data as described for efficacy measures in Section 12.2.7. More detailed analytical methods will be described in the SAP.

12.2.9. Safety Analyses

All safety data will be descriptively summarized by treatment groups and analyzed using the mITT population.

For the purposes of calculating changes from baseline during Part A and Part B treatment, baseline may be considered as the original baseline for Part A – prior to any study drug received – or at the visits that mark the transition between treatments received, depending on the purpose of the summary or comparison being made. Summaries within Parts A and B will be conducted by treatment group used within each respective part. Additional summaries by treatment group that continue unchanged across multiple parts of the study will be conducted, as appropriate.

Treatment-emergent adverse events are defined as AEs that first occurred or worsened in severity after the first dose of study treatment. AEs will be considered treatment emergent for nonresponders assigned to baricitinib if the AEs first occurred or worsened in severity after the visit at which rescue therapy is assigned. The number of TEAEs as well as the number and percentage of patients who experienced at least 1 TEAE will be summarized using Medical Dictionary for Regulatory Activities (MedDRA) for each system organ class (SOC) (or a body system) and each preferred term by treatment group. TEAEs will also be summarized by relationship to treatment and by severity within each treatment group. Serious adverse events (SAEs) and AEs that lead to study drug discontinuation will also be summarized by treatment

group. Fisher's exact test will be used to perform the statistical comparisons between baricitinib and placebo.

All clinical laboratory results will be descriptively summarized by treatment group. Individual results that are outside of normal range will be flagged in data listings. Quantitative clinical hematology, chemistry, and urinalysis variables obtained at the baseline to postbaseline visits will be summarized as changes from baseline by treatment group and analyzed using ANCOVA with treatment and baseline value in the model. Categorical variables, including the incidence of abnormal values and incidence of AESIs, will be summarized by frequency and percentage of patients in corresponding categories. Shift tables will be presented for selected measures.

Observed values and changes from baseline (predose or screening if missing) for vital signs and physical characteristics will be descriptively summarized by treatment group and time point. Change from baseline to postbaseline in vital signs, QIDS-SR₁₆, and body weight will be analyzed using ANCOVA with treatment and baseline value in the model.

The incidence and average duration of study drug interruptions will be summarized and compared descriptively among treatment groups. Various techniques may be used to estimate the effects of study drug interruptions on safety measures. Further analyses may be performed and will be planned in the SAP.

Data collected after initiation of rescue therapy will be summarized as appropriate.

12.2.10. Subgroup Analyses

Subgroups analyses comparing baricitinib to placebo will be performed using ACR20, ACR50, HAQ-DI and DAS28-hsCRP at Week 12, Week 24, and mTSS at Week 24. Subgroups to be evaluated will include country, renal function, background therapy, joint erosion status, gender, age, race, etc. Any other additional subgroups will be defined in the SAP.

For ACR20 and ACR50 analyses at Week 12 and Week 24, a logistic regression model will be used with treatment, subgroup, and treatment by subgroup interaction included as factors.

For the change from baseline to Weeks 12 and Week 24 in HAQ-DI score and DAS28-hsCRP and to Week 24 in mTSS, an ANCOVA model will be used with treatment, baseline score, subgroup, and treatment by subgroup interaction included as factors.

Further definitions for the levels of the subgroup variables, the analysis methodology, and any additional subgroup analyses will be defined in the SAP. Because this study is not powered for subgroup analyses, all subgroup analyses will be treated as exploratory.

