12.1. Determination of Sample Size

Approximately 288 patients (144 in baricitinib, 144 in placebo) will provide:

- 99% power to detect a difference between the baricitinib and placebo treatment groups in ACR20 response rate (60% versus 35%) at Week 12 based on a 2-sided chi-square test at a significance level of 0.05.

The sample size and power estimates were obtained using nQuery[®] Advisor 7.0.

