12.2. Statistical and Analytical Plans

12.2.1. General Considerations

All statistical tests of treatment effects will be performed at 2-sided significance levels of 0.05, unless otherwise stated. Treatment comparisons of discrete efficacy variables will be made using a logistic regression analysis with country, joint erosion status (1-2 joint erosions plus seropositivity vs at least 3 joint erosions) and treatment group in the model. The proportions and 95% CI will be reported. Treatment comparisons of continuous efficacy variables will be made using analysis of covariance (ANCOVA) with country, treatment group, joint erosion status and baseline value in the model. Type III sums of squares for the least-squares (LS) means will be used for the statistical comparison; the 95% CI will also be reported.

When a restricted maximum likelihood (REML)-based mixed model for repeated measures (MMRM) is used, the model will include the fixed, categorical effects of treatment, country, joint erosion status, visit, treatment-by-visit-interaction, as well as the continuous, fixed covariates of baseline score and baseline score-by-visit-interaction. An unstructured (co)variance structure will be used to model the within-patient errors. If this analysis fails to converge, other structures will be tested. Type III sums of squares for the LS means will be used for the statistical comparison; the 95% CI will also be reported. Treatment group comparisons at Week 12 and all other visits will be tested. Further details on the MMRM will be described in the statistical analysis plan (SAP).

Fisher's exact test will be used for all AEs, discontinuation, and other categorical safety data. Continuous vital signs and other continuous safety variables including laboratory parameters will be analyzed using ANCOVA with treatment and baseline value in the model.

Analysis Population:

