6.2. Adjustments for Covariates

The covariates used in the parametric statistical model (ANCOVA) of continuous data generally will include the parameter value at baseline. Inclusion of baseline in the ANCOVA model provides estimated adjusted (least squares) means for each treatment reflecting averages for the average baseline patient. Other independent variables that will be included in the models for efficacy and health outcomes analyses to adjust estimates of treatment effect include the stratifying variables country and joint erosion status. When the patient number in each country is deemed small (ie, $n < 30$), countries will be combined into regions (ie, East Asia and Central America). The independent variables used in the logistic regression models will include country/region and joint erosion status (refer to Section 6.1). The stratification variables used in the analyses will be derived based on electronic case report form (eCRF) data and x-ray data collected by Bioclinica.

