6.15. Subgroup Analyses

Subgroup analyses comparing baricitinib to placebo will be performed on the mITT population using ACR20, ACR50, DAS28-hsCRP <2.6 , DAS28-hsCRP ≤ 3.2 , SDAI ≤ 3.3 , HAQ-DI Improvement ≥ 0.22 , and change from baseline in HAQ-DI and DAS28-hsCRP at Week 12 (Visit 7) and Week 24 (Visit 11) and using mTSS at Week 24 (Visit 11).

The following subgroups (but not limited to only these) will be categorized into disease-related characteristics and demographic characteristics and will be evaluated:

- Gender (Male, Female)
- Age (<65 years, ≥ 65 years)
- Country
- Screening renal function status: impaired (eGFR <60 mL/min/1.73 m 2) or not impaired (eGFR ≥ 60 mL/min/1.73 m 2)
- Joint erosion status (1-2 joint erosions plus seropositivity, at least 3 joint erosions)
- Background therapy (MTX only, MTX + other cDMARDs)
- Baseline weight (\leq median, $>$ median)
- Baseline BMI category (\leq median, $>$ median)
- Baseline BMI category (<18.5 kg/m 2 , ≥ 18.5 to <25 kg/m 2 , ≥ 25 to <30 kg/m 2 , ≥ 30 kg/m 2)
- Baseline disease severity (DAS28-hsCRP ≤ 5.1 , DAS28-hsCRP > 5.1)

The subgroup analyses for categorical outcomes will be performed using logistic regression. The model will include the categorical outcome based on NRI as the dependent variable and treatment, subgroup, and treatment-by-subgroup interaction as explanatory variables. The treatment-by-subgroup interaction comparing treatment groups will be tested at the 0.1 significance level. The p-value from the logistic regression will be reported for the interaction test. When logistic regression sample size requirements (<5 responders in any category for any subgroup) are not met, the p-value will not be produced. Counts, percentages, the odds ratio, and the 95% CI of the odds ratio within a subgroup obtained from the same model with the subgroup and interaction terms removed will be presented for comparing treatment group differences. For significant findings, further analytical inspection will be made to assess the plausibility of any impact on drug effect.

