An ANCOVA will be used to analyze the change from baseline based on mBOCF in HAQ-DI and DAS28-hsCRP at Week 12 and at Week 24, and based on linear extrapolation in mTSS at Week 24 with baseline, treatment, subgroup, and treatment-by-subgroup as explanatory variables. The treatment-by-subgroup interaction will be tested at the 0.1 significance level. The LS mean, LS mean difference, SE, and 95% CI within subgroups obtained from the same ANCOVA model with the interaction and subgroup terms removed will be presented.

Descriptive statistics will be provided for each treatment and stratum of a subgroup as outlined, regardless of sample size. In addition, the aforementioned formal statistical analysis will be performed when there are a minimum of 30 patients per treatment group per stratum of the subgroup. In some cases, select strata within the subgroups may need to be pooled in order to

achieve 30 patients per treatment group per stratum for analysis. The descriptive and analysis statistics for the pooled strata will be displayed in addition to the descriptive statistics for the initial strata. The detailed pooling strategy is described below:

- For subgroups with 2 strata: gender, age, screening renal function status, background therapy, joint erosion status, baseline weight, baseline BMI category, baseline disease severity (DAS28-hsCRP) —If 1 of the strata fails to meet the required minimum number, then no formal statistical analysis will be provided.
- Country (3 strata)—Pool patients from Argentina and Brazil if needed. If after pooling, 1 of the strata fails to meet the required minimum number, then no formal statistical analysis will be provided.
- Baseline body mass index (four strata) —If one of the strata fails to meet the required minimum number, the stratum will be pooled with the next contiguous heavier BMI stratum, except for the heaviest BMI stratum which will be pooled with the next heaviest BMI stratum. The pooling will continue until all strata including pooled strata meet the required minimum number.

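### The subgroup models leave out country/region and joint erosion status, unlike the plan's other efficacy models of the same endpoints; the cost is small and the remedy cheap

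*Protocol*

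**What the plan says.** **General rule.** Randomisation is stratified by country and joint erosion status (Protocol 9.3, SAP 5.3). For binary efficacy endpoints, Protocol 12.2.1 says comparisons "will be made using a logistic regression analysis with country, joint erosion status" and treatment; its ANCOVA rule has the same two factors plus baseline. SAP 6.1 repeats both rules. SAP 6.2 says "The independent variables used in the logistic regression models will include country/region and joint erosion status" and states no exception for subgroups.

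**Subgroup rule.** Protocol 12.2.10 specifies, for ACR20 and ACR50, that "a logistic regression model will be used with treatment, subgroup, and treatment by subgroup interaction included as factors". For HAQ-DI, DAS28-hsCRP and mTSS it adds only the baseline score. SAP 6.15 agrees: the ANCOVA is fitted "with baseline, treatment, subgroup, and treatment-by-subgroup as explanatory variables". Estimates within a subgroup level are then "obtained from the same model with the subgroup and interaction terms removed will be presented" (logistic; the ANCOVA wording is equivalent). That leaves treatment alone for the odds ratio, and baseline plus treatment for the LS mean difference.

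**Status.** Protocol 12.2.10 calls all subgroup analyses exploratory and unpowered. SAP 6.15 requires at least 30 patients per arm per level for formal analysis. Country and joint erosion status are themselves listed subgroups.

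**The concern.** A trial that stratifies its randomisation by two factors normally carries them into its models, and this plan does so in its main efficacy analyses. Exploratory status does not explain the exception. SAP 6.16 is also exploratory and keeps both factors for the same endpoints: mTSS change at Week 24, ACR20 and ACR50 through Week 24, and change in HAQ-DI and DAS28-hsCRP.

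Two things are at stake, both modest. For continuous endpoints, leaving out prognostic factors leaves their variation in the residual and can widen intervals. For binary endpoints, the overall odds ratio (SAP 6.11.1) is conditional on country/region and erosion status, while the within-subgroup odds ratios are not. Odds ratios are non-collapsible, so the two differ even when the treatment effect is the same in every patient. Anyone comparing a subgroup odds ratio with the overall one could take part of that gap for a weaker effect.

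**Working it through.** **Inputs from the documents.** Protocol 12.1 plans 288 patients, 144 per arm, and assumes Week 12 ACR20 rates of 60% on baricitinib and 35% on placebo; its stated power of 99% is computed "based on a 2-sided chi-square test at a significance level of 0.05". The minimum level size of 30 per arm is from SAP 6.15. The documents give no prognostic strength or prevalence for country or erosion status, so those are assumed and shown as ranges.

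**Step 1: reproduce the stated power.** Mean rate 0.475.
- Null SE = sqrt(2 × 0.475 × 0.525 / 144) = 0.0589.
- Alternative SE = sqrt((0.60 × 0.40 + 0.35 × 0.65) / 144) = 0.0570.
- Power = Φ((0.25 − 1.96 × 0.0589) / 0.0570) = 0.991, which matches the plan's 99%.
- Implied unadjusted odds ratio = (0.60/0.40) / (0.35/0.65) = 2.786.

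**Step 2: binary endpoints.** Take two binary factors with prevalences 20% and 50%, each with the same odds ratio for response. Hold the arm-level rates at 35% and 60%, and solve for the treatment odds ratio conditional on both factors. The gap is 1 − 2.786 / adjusted OR.

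| Assumed factor OR | Adjusted OR | Gap | SE(log OR), 144/arm | z | SE(log OR), 30/arm | z |
|---|---|---|---|---|---|---|
| Factors omitted | 2.786 | – | 0.2438 | 4.201 | 0.5342 | 1.918 |
| 1.25 | 2.800 | 0.5% | 0.2446 | 4.210 | 0.5359 | 1.921 |
| 1.5 | 2.833 | 1.7% | 0.2463 | 4.228 | 0.5395 | 1.930 |
| 2 | 2.924 | 4.7% | 0.2508 | 4.278 | 0.5495 | 1.953 |
| 3 | 3.135 | 11.1% | 0.2607 | 4.382 | 0.5712 | 2.000 |

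The most extreme case tried (both prevalences 50%, factor OR 4) gives 3.473, a gap of 19.8%. A second calculation used three-country mixes and fixed the adjusted OR at 2.80. It gave unadjusted values of 2.78, 2.73, 2.63 and 2.52, that is 1% to 10% lower.

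Omitting the factors makes both the log odds ratio and its standard error smaller. Simulation at 72 per arm (1,500 replicates, factor OR 2) agrees: mean log OR 1.031 with SD 0.349 unadjusted, against 1.098 with SD 0.369 adjusted. The loss is a small fall in z, not precision. For the 0.1-level interaction test, simulated power was 0.2 to 1.0 points higher with adjustment. Monte Carlo error on a single estimate from 1,500 trials is about 0.8 to 1.3 points, so only the direction should be taken from that.

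**Step 3: continuous endpoints.** SE ratio, omitted over included, is 1/sqrt(1 − R²), where R² is the assumed share of residual variance explained.
- R² of 1%, 2%, 5%, 10%: 1.005, 1.010, 1.026, 1.054.
- All-patient interaction model, n = 288, 5 parameters rising to 8 (two for country, one for erosion). The ratio included over omitted is sqrt((1 − R²) × 283/280) = 0.995, 0.980, 0.954 at R² of 2%, 5%, 10%. At 1% it is 1.000, so the gain is gone.
- Factors added instead to a fit within one level of 30 per arm, losing 2 df: the omitted-factor SE differs by −1.3%, −0.8%, +0.8%, +3.5%. The gain there can vanish or reverse.

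**The case against.** The case for leaving the plan alone is reasonable. Protocol 12.2.10 and SAP 6.15 agree on the reduced models, and a specific rule overrides a general one, so a programmer has nothing to resolve. At 30 per arm, exp(1.96 × 0.534) is about 2.85, so a subgroup odds ratio of 2.79 has an interval of roughly 0.98 to 7.9; a shift of a few per cent cannot be seen against that. No side-by-side display of subgroup and overall odds ratios is planned, and the counts and percentages also presented let a reader work out response differences directly. Contrasts from one all-patient model assume common covariate effects (and, for ANCOVA, a common baseline slope) across subgroup levels, which separate fits do not. SAP 6.15 also includes rarer outcomes such as SDAI remission, where extra factors give the sparse-responder rule in SAP 6.1 more chances to apply.

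All of this stands as a limit on importance. It does not supply a reason for the omission, and SAP 6.16 shows that the adjusted model is otherwise the plan's choice for these endpoints.

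Four stronger readings are tempting and not supported:
- That subgroup estimates lose precision generally. Step 2 shows the opposite for the logistic models.
- That every efficacy model carries the two factors. Diary and tablet stiffness duration use Wilcoxon and Hodges-Lehmann methods without covariates (SAP 6.13.1.2, 6.16.1.1).
- That both factors are always dropped. In the country and erosion subgroups, one of them is the subgroup term, so only the other is missing.
- That the documents contradict each other. This is an agreed exception without a stated rationale.

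**Conclusion.** The omission is real, appears in both documents, and departs without explanation from the general covariate rule and from SAP 6.16. It is a minor point.

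For HAQ-DI, DAS28-hsCRP and mTSS, intervals may be about 0.5% to 5% wider than needed if R² is 1% to 10%, and less once degrees of freedom are counted. For binary endpoints, precision is not lost. A little power is, and the treatment-only subgroup odds ratios tend to lie roughly 0.5% to 10% nearer to 1 than the adjusted overall odds ratio under a constant effect (more if the factors are very strong). The tendency can be offset where the subgroup variable is itself prognostic, because a within-subgroup estimate conditions on it.

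Every size here rests on assumed prognostic strength and on the trial-wide 35% and 60% rates holding within subgroups. Primary inference, alpha and sample size are untouched.

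**What to change.** In SAP 6.15, and in Protocol 12.2.10 for consistency, add country/region and joint erosion status to the all-patient logistic and ANCOVA interaction models, omitting a factor when it is the subgroup. Take within-subgroup odds ratios and LS mean differences as contrasts from that model, not from refits within each level; this avoids sparse country cells and the degrees-of-freedom loss seen at 30 per arm. For rare binary outcomes where the responder-count rule is not met, keep the unadjusted model and show an unadjusted overall odds ratio beside the subgroup ones.

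The cost is wording and two extra factors in the subgroup code, with no new data. Protocol 12.2.1 requires an amendment only when a principal feature changes, so a justified SAP change appears sufficient, with the protocol text aligned at the next opportunity. The price is the common-covariate-effect assumption, and a sparse-responder rule that may apply slightly more often. If the sponsor prefers the reduced models, SAP 6.2 should state the exception and its reason, and the unadjusted overall odds ratio should accompany the subgroup results.
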